#### 6.2.2 Blinding procedures

Given the nature of the intervention, NH staff (pharmacist, physician and nurses) cannot be blinded to the allocation. As the data collected differ between participants in the intervention and control groups,

investigators will not be blinded either.

Thus, only the statistician will be blinded: he will not have access to the raw data, and all data extracted for analysis will be communicated to him with groups coded A and B. Unblinding will occur only after analysis completion. Descriptive statistics will be performed after completion of the primary analysis, as the data relative to the treatment changes enacted in the intervention group will allow the differentiation of the groups by the statistician.

### **6.2.3 Other methods of minimising bias**

Assessment of quality of life will be made using the EQ-5D-5L, which has been validated in large studies across Europe [45], and tested in NH residents with cognitive impairment [46].

Assessment of the burden of care will be made with the NeuroPsychiatric Index – Nursing Home, a validated questionnaire for the assessment of changes in patient's behaviour and the impact of said changes on carer and staff [47].

## **6.3 Unblinding Procedures**

As participants, NH care teams and the investigators will not be blind to the allocation, no unblinding procedure is necessary: the NH care team, without regard to the allocation of participants, will deal with all eventual adverse events resulting from the intervention. In addition, as no intermediate analyses are planned, no event will trigger the need for unblinding before study completion.

# **7. STUDY POPULATION**

The study will be conducted in the NH allocated to the intervention group of the OLD-NH-QC-DeMo study (see section 3.1, page 13 for details and Annex 7 for the list of eligible NHs).

### **7.1 Eligibility criteria**

All residents of the NHs mentioned in Annex 7 are eligible for participation if:

- They are 65 years old or older;
- They take 5 or more regular drugs;
- They have been resident of the NH for at least 4 months at inclusion;

If the NH head nurse and a resident's treating physician judge that discussing the possibility of deprescribing will lead to their destabilisation, this resident will be excluded from recruitment.

### **7.2 Screening and recruitment**

Screening for participants will take place in the NH and will be performed by the NH care team (treating physician, head nurse and pharmacist). It will consist of two phases: ranking and screening.

Ranking: pharmacists will rank the residents in decreasing order of number of regular drugs prescribed, based on the treatment regimen recorded in the patients' file at the time of ranking.

Screening: with the ranking performed, the NH care team will decide which residents will be excluded from recruitment, as the discussion of deprescribing with them could destabilise them. After screening, a list of residents eligible for recruitment, ranked in decreasing order of PIMs use, will be prepared by the pharmacist.

Recruitment of residents will be made by the nurse responsible for the study in the NH, using the information and consent form (Annex 1 and Annex 2). Participation will initially be offered to a number of residents equal to 20% of the capacity of the NH (number of beds); residents or their representative will be given at least 24 hours of reflexion to decide whether to enter the study. For every resident declining to enter, participation will be offered to the next eligible resident, following the ranking list. Recruitment will continue until 20% of the population of the NH has been recruited, or until participation has been offered to all residents.

No compensation, monetary or otherwise, will be offered to participants.

### **7.3 Assignment to study groups**

After recruitment, participants will be randomised between control and intervention groups. Randomisation will be made using the inclusion CRF; after randomisation, the allocation group will be recorded in a NH-specific list, to be stored with the study documents. This list will comprise the name of the

participants, their identifying code and allocated group. Allocation will be communicated to the treating physician and the participants.

## **7.4 Criteria for withdrawal of participants**

Participants, or their representative if applicable, can withdraw from the study at any time, without justification.

The NH care team can withdraw participants from the study if they estimate that the safety of the participant is not guaranteed anymore. However, we do not anticipate this to happen: if the clinical status of the participant does not allow for treatment alterations, the NH care team will simply not enact the planned treatment modifications. In addition, a stopped or tapered drug can be reintroduced at any time during the study. The treating physician will indeed remain in control of the participant's care at all time.

Participants withdrawing during the study will not be replaced.

# **8. STUDY INTERVENTION**

## **8.1 Identity of Investigational Intervention**

### **8.1.1 Experimental Intervention**

The intervention tested in this study is a medication review focused on deprescribing, followed by the construction and implementation of a deprescribing plan. A medication review is "a structured evaluation of a patient's medicines with the aim of optimising medicines use and improving health outcomes." [48] This review will take into account the clinical situation of the participant, including pathologies, disabilities, current drug regimen, and her / his therapeutic and life goals.

The responsible pharmacist of the NH where the participant resides will perform the medication review. They will receive education on the realisation of medication review prior to the study by attending the "Medication review" module of the Certificate in Advanced Studies "Pharmacie Clinique: prestations dans les soins de base" . Through the study, pharmacists will be able to solicit the clinical advices of the *Centre de Pharmacie Communautaire* Pharmaceutical Assistance team for performing of the reviews.

The results of the review will be structured propositions of drug regimen modification, according to the clinical situation of participant and the risk/benefit balance of each prescribed drug for her-/him-self. These propositions will include regimen modifications (modification of galenic forms or administration time or frequency), withdrawal or tapering of non-beneficial drugs (deprescribing), and introduction of new drugs in case of prescribing omission (sub-optimal treatment). These propositions will be discussed with nurse and treating physician of the NH, with the goal to create a deprescribing plan that will be proposed to the participant. The propositions resulting from the review and the deprescribing plan will be prepared following the model documents in Annex 8.

### **8.1.2 Comparator**

The comparator will be usual care, as routinely provided in the NHs where the study takes place.

### **8.1.3 Packaging, Labelling and Supply (re-supply)**

Not applicable to this study.

### **8.1.4 Storage Conditions**

Not applicable to this study.

## **8.2 Administration of experimental and control interventions**

### **8.2.1 Experimental Intervention**

See section 8.1.1 and Annex 8 for details on the intervention.

### **8.2.2 Control Intervention**

See section 8.1.2 for details on the comparator.

---

<https://www.unige.ch/formcont/cours/cas-pharmacie-clinique-prestations-dans-les-soins-de-base-2018>

### **8.3 Dose / Device modifications**

Not applicable to this study.

### **8.4 Compliance with study intervention**

As part of the monitoring, (see section 12.3, page 30), the investigators will conduct a weekly check of the progress of inclusion, intervention and data collection. Regular consultation of the CRFs and uploaded documents will ensure that any deviation from the protocol are detected early and that corrective measures can be implemented in a timely manner.

### **8.5 Data Collection and Follow-up for withdrawn participants**

No further data collection will occur for participants withdrawing from the study. Data already collected will be anonymised and used in the analysis.

Withdrawn participants will be monitored as usual by the NH care team.

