## **2.7 Patient Information and Informed Consent**

Each participant, or her/his legal representative if applicable, will be informed of the nature of the study, its purpose, the procedures involved, the expected duration, the potential risks and benefits and any discomfort it may entail. Each participant or his/her representative will be informed that the participation in the study is voluntary, that he/she may withdraw from the study at any time, and that withdrawal of consent will not affect his/her subsequent medical assistance and treatment.

The participant will be informed that his/her medical records may be examined by authorised individuals other than their treating physician.

All participants for the study will be provided a participant information and consent form (see Annex 1) describing the study and providing sufficient information for participant to make an informed decision about their participation in the study. For participants unable to consent because of cognitive impairment, the consent of their legal representatives will be necessary (see Annex 2). Participants or their representative will be given at least 24 hours to review the documents before deciding to enrol or not in the study.

The formal consent of a participant, or of her/his representative, using the approved consent form, will be obtained before the participant is submitted to any study procedure.

The participant or her/his representative, after being given enough time to read and consider the statement, will read and date the informed consent form, and will be given a copy of the signed document. The consent form will also be signed and dated by the investigator's representative at the same time as the participant sign, and it will be retained as part of the study records.

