### 9.2.5 Assessments in participants who prematurely stop the study

In case of participant death before completion of follow-up, the follow-up CRF (staged for completion at visit 2) will be completed within 7 days by the pharmacist and nurse. For the assessment of the treatment plan regarding PIM status, the pharmacist will take into account the treatment plan of the day preceding death. No information will be collected regarding quality of life and common complaints.

If a participant is hospitalised at the date of the follow-up visit, the same procedure as for the participant having died is applied. The treatment plan of the day preceding the hospitalisation will be taken into account.

If a participant wishes to stop the study before the follow-up visit, she/ he will be offered to complete the quality of life and common complaints questionnaire before exiting the study.

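### Section 8.5 ends data collection even for residents the care team withdraws for safety, so their 4-month PIM count and some later harms are missing from an intention-to-treat analysis

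*Combined protocol and SAP*

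**What the plan says.** Section 7.4 gives two routes out of the study. The resident or representative may leave at any time. Separately, "The NH care team can withdraw participants from the study if they estimate that the safety of the participant is not guaranteed anymore". The protocol thinks the second route unlikely ("However, we do not anticipate this to happen") and gives a reason: if a resident's condition rules out changes, "the NH care team will simply not enact the planned treatment modifications".

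Section 8.5, whose heading covers withdrawn participants in general, then sets one rule: "No further data collection will occur for participants withdrawing from the study". It adds that "Data already collected will be anonymised and used in the analysis", and that "Withdrawn participants will be monitored as usual by the NH care team".

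Section 9.2.5 covers three kinds of early stop:

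- **Death:** the follow-up CRF is completed and PIMs are assessed on the treatment plan from the day before.
- **In hospital at the follow-up date:** the same procedure applies, using the plan from the day before admission.
- **A resident who wishes to stop:** he or she "will be offered to complete the quality of life and common complaints questionnaire before exiting the study". No medication plan, PIM assessment or harms are mentioned.

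A care-team withdrawal is not on this list. Section 11.4.1 states an intention-to-treat approach. Section 11.5 offers multiple imputation when outcome data are missing at random in more than 5% and less than 40% of participants.

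**The concern.** Stopping data collection is justified when a resident withdraws consent to it. A care-team decision on safety grounds is a different event. Section 2.7 treats withdrawal of consent as an act of the resident or representative ("withdrawal of consent will not affect his/her subsequent medical assistance and treatment"), and nothing in 2.7 or 7.4 says that a care-team withdrawal cancels the resident's agreement to the use of data. For this group the loss looks like a choice of the plan, not an ethical requirement.

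The residents concerned are also not a random subset. The criterion is safety, and 6.2.2 says that the staff who apply it know the allocation. Their withdrawal may be related to the intervention and to the outcome, which makes missing at random doubtful. At stake are the primary outcome for those randomised residents and part of the harms data, in a trial with a stated safety objective (4.5) and no data safety monitoring committee (1.6).

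**Working it through.** **1. Is there a rule for care-team withdrawals elsewhere?** The main sentence of 8.5 could be read as covering only residents who withdraw themselves. Its heading and its last sentence speak of withdrawn participants, which includes those withdrawn by others. On the wider reading, collection stops for them. On the narrower reading, neither 8.5 nor 9.2.5 tells the team what to collect. Both readings need an amendment.

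**2. Could the data be obtained?** Section 12.1.2 names the nursing home record as the source for the medication plan, hospitalisations, falls, restraints and death. Section 8.5 says usual monitoring goes on. The PIM count is not in that record, but 9.2.1 derives it from pathologies and treatments entered in the STOPP/START tool, and 9.2.5 already does so without the resident after death or hospitalisation. One limit applies: in the intervention arm, baseline collection waits for the validated plan, up to 2 months (6.1, 9.3.1). A resident withdrawn before Visit 1 therefore needs a baseline plan as well, or there is no change score.

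**3. Which harms lack another route?** Section 10.2.1 requires all SAEs within a week on a separate CRF and states no exception for withdrawn residents. Section 10.1 limits adverse events to those where a causal link with the intervention cannot be excluded. Non-serious falls, restraint days, and deaths or hospitalisations not reported as SAEs depend on the follow-up CRF alone.

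**4. Planned size.** Section 11.2: half of 18 homes = 9; 9 × 59 × 0.20 = 106.2, which reproduces the stated 106. Section 6.1: 10 × 50 × 0.20 = 100. At 1:1 allocation the arms hold about 53 or 50.

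**5. Imputation threshold (11.5).** Missing values from any cause count towards it.

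| Missing | of 100 | of 106 | Imputed? |
|---|---|---|---|
| 5 | 5.0% | 4.7% | no |
| 6 | 6.0% | 5.7% | yes, if missing at random |

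**6. Illustrative effect on the primary comparison.** Assumptions: 1 to 5 care-team withdrawals, and a mean change in PIMs that differs by 1 from that of the other residents. If the missing residents are left out:

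shift in group difference = (share missing in arm 1 − share missing in arm 2) × difference in mean change

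- Even split: about 0
- One resident, arm of 53: 1/53 × 1 = 0.019
- Five in one arm of 53: 5/53 × 1 = 0.094
- Five in one arm of 50: 5/50 × 1 = 0.10

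The documents give no withdrawal rate, no split by arm and no difference in outcome, so the sign is unknown.

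**7. Workload.** Planned PIM analyses: 2 × 106 = 212. One analysis for each of 1 to 5 residents is 1/212 = 0.5% to 5/212 = 2.4%. Two each, if baseline is also outstanding, is 2/212 = 0.9% to 10/212 = 4.7%. All were planned for those residents anyway.

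**The case against.** The strongest objection is that the group is almost empty by design. Planned changes can be left undone, stopped drugs can be restarted (7.4, 8.6), and residents may refuse single items of the plan (6.1). All of these residents stay in follow-up. The usual failure of intention to treat, losing people because they stop the intervention, is therefore largely absent. This stands, and it keeps the point modest. It does not remove the route that 7.4 leaves open.

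It can also be said that declaring intention to treat is about analysing by allocation, and that 11.5 deals with missing values. This is true in part. But imputation under missing at random is a weak substitute for a value that can be derived from an existing record, and with five or fewer missing it does not apply.

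Several stronger readings are tempting but not supported:

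- **All later harms are lost.** Section 10.2.1 makes no exception for withdrawn residents, so SAEs may still be reported. What the text shows is an unresolved tension with 8.5.
- **The bias favours the intervention.** This requires assuming that withdrawals fall in one arm and that those residents had no PIM reduction. The documents support neither.
- **Withdrawn residents count as event-free in the mortality and hospitalisation rates.** Section 5.4 does not say so.
- **Anonymisation under 8.5 blocks later extraction, or harms up to exit go unrecorded.** The timing of anonymisation is not stated, and the follow-up CRF (Annex 10) is not shown.

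That a care-team withdrawal leaves consent intact is itself an inference. The consent forms (Annexes 1 and 2) are not shown and may set other terms.

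**Conclusion.** The point holds as a gap in a stated rule, and it is worth correcting. Following 8.5 as written, a resident withdrawn by the care team for safety would have no 4-month medication plan or PIM count. Later falls, restraint days, and deaths or hospitalisations not reported as SAEs would be uncollected. The source record continues to exist throughout.

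The effect is probably very small: from about zero to 0.10 PIM in the illustration, with the upper end needing five withdrawals, all in one arm of 50. The number, the split and the 1-PIM difference are assumptions, and the direction is unknown. The documents give no basis for a count of missed harms. The case for change rests on the text and on the low cost of the remedy, not on an expected large bias. Confidence is medium, mainly because the consent forms are not shown.

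**What to change.** Amend 8.5 and 9.2.5 to separate leaving the study from withdrawing consent to data use. A participant withdrawn by the care team, or who stops without withdrawing consent to data use, should stay in follow-up from the nursing home record:

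- the medication plan with the pharmacist's PIM assessment at 4 months, and also at baseline if withdrawal came before Visit 1;
- death, hospitalisation, falls and restraint days to the end of the 4 months.

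Reconcile 8.5 with 10.2.1 by stating whether SAE reporting continues after withdrawal. Check the wording against Annexes 1 and 2 and align them if needed. The care team's freedom to withdraw a resident is unaffected.

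The cost is protocol wording, possibly a sentence in the consent forms, and one or two record extractions and PIM analyses per such resident, done by staff who already do them. The downside is some work for nursing home teams whose load 8.6 seeks to limit.

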### **8.6 Trial specific preventive measures**

All interventions part of usual care deemed necessary by the NH care team are allowed before and during the trial, in both arms. Specifically, modifying or stopping a treatment is allowed in the patients allocated to the control group, and restarting a withdrawn treatment is allowed in the intervention group.

The interventions other than the ones specified in the deprescribing plan will not be collected, as they are of no interest to the study outcome and would impose too big a workload on the NHs care team.

### **8.7 Concomitant Interventions**

See section 8.6

### **8.8 Study Drug / Medical Device Accountability**

Not applicable to this study.

### **8.9 Return or Destruction of Study Drug / Medical Device**

Not applicable to this study.

## **9. STUDY ASSESSMENTS**

### **9.1 Study flow chart**

See page 9 for the study flow-chart.

### **9.2 Assessments of outcomes**

#### **9.2.1 Assessment of primary outcome**

The primary outcome is the change in the number of PIMs between baseline and 4 months. To identify PIMs, NH pharmacists will use the online implementation of the STOPP/START tool provided by the French *Caisse Nationale d'Assurance Maladie*, found at <https://aide-a-la-decision.ameli.fr/revision-ordonnance/>. This tool requires the pharmacist to enter the patients' pathologies and treatments, but no other information. No information are stored on the website once the analysis has been performed. An example of such analysis can be found in Annex 9.

The pharmacist will then upload the PIM report and the participants' treatment plan into the CRF (see Annex 10). The investigators will then transcribe the medication plan for each participant into an investigator-reserved CRF (see Annex 11), including the PIM status of each treatment. This analysis will be made at baseline and 4 months.

The total number of PIMs at every time point for each participant will then be computed by the investigators, and difference in the number of PIMs between baseline and follow-up computed for each participant.

---

 Authorisation for the use of this tool has been granted by its co-concepteur, [name].

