After randomisation, the record of participants allocated to the intervention group will be searched by the nurse responsible for the study in the NH ("study nurse") for clearly stated objectives of care. If no objectives are present in the record, the referent nurse for this participant will be interviewed by the pharmacist to clarify these objectives. The referent nurse will also provide a list of drugs taken by the participant without supervision of the NH staff (self-medication). Using this information and the content of the participant's records in the NH and in the pharmacy, the pharmacist will then conduct the medication review according to the formation received; the medication review process is described in chapter 8, page 20. Based on the results of the medication review, a deprescribing plan will be decided by the NH care team (head nurse, physician(s) responsible for the resident(s), and pharmacist). This plan will also include proposition for the introduction of new drugs if prescription omissions (sub-optimal treatment) are detected by the medication review. Each item of this plan will then be presented for validation to the participant or her/his representative. Once validated, baseline data collection will occur and the deprescribing plan will be implemented.

Participants allocated to the control group will receive usual care. Baseline data collection for them will occur after inclusion. Follow up data collection will occur 4 months after baseline data collection for both groups. The duration of the study will be 4 months for the participants allocated to the control group. For participants allocated to the intervention group, the realisation of the medication review by the pharmacist, the discussion of its results with the treating physicians, the creation of the deprescribing plan, and its discussion with the participant will induce a delay before baseline data collection, estimated of maximum 2 months; thus, the total duration of the study could be up to 6 months in this group. Participants allocated to both groups will be monitored as usual by the NH care team (treating physician and nurses) during and after the duration of the study. In addition, the NH care team will mention specific monitoring measures in the deprescribing plan, according to the drugs being deprescribed and the clinical situation of the participant.

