### 9.3.1 Visit 1: Baseline data collection

Timeframe: immediately after inclusion for control group; at the time of implementation of the deprescribing plan for the intervention group.

Action performed with the participant:

- Completion of the baseline EQ-5D-5L questionnaire (using the paper version), by the pharmacist and the nurse, in presence of the participant or her/his representative;
- Completion of the baseline common complaints questionnaire (see Annex 5);
- Planning of the follow-up visit.

Action performed after the visit, in the absence of the participant:

- Upload of the baseline EQ-5D-5L questionnaire into the CRF;
- Upload of the baseline common complaints questionnaire into the CRF;
- Upload of the current medication plan into the CRF;
- Performing and upload of the PIM assessment, as described in section 9.2.1;
- Upload of the deprescribing plan (see Annex 8) into the CRF;
- Completion of the NPI-NH questionnaire (see Annex 6) by the nurse referent for the participant, and upload by the pharmacist into the CRF.

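### The unblinded pharmacist who delivers the intervention also scores the primary outcome in both arms, and so holds a PIM report on each control at the start of follow-up

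*Combined protocol and SAP*

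**What the plan says.** Section 9.2.1 makes the NH pharmacist the assessor: "To identify PIMs, NH pharmacists will use the online implementation of the STOPP/START tool". On inputs it says "This tool requires the pharmacist to enter the patients' pathologies and treatments, but no other information", and on timing "This analysis will be made at baseline and 4 months". The pharmacist uploads the resulting report with the treatment plan. The investigators transcribe the plan with each drug's PIM status and compute the totals.

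The task lists in 9.3.1 and 9.3.2 both contain the step "Performing and upload of the PIM assessment, as described in section 9.2.1", with no restriction by arm. For controls, Visit 1 is immediately after inclusion. For the intervention arm it is when the deprescribing plan is put into effect.

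Section 8.1.1 gives the intervention to the same person: "The responsible pharmacist of the NH where the participant resides will perform the medication review". Section 6.2.2 leaves NH staff unblinded. It also leaves the investigators unblinded, with the reason "As the data collected differ between participants in the intervention and control groups"; only the statistician is blinded. Section 6.2.1 randomises participants 1:1 within each NH. Section 8.1.2 defines the control condition: "The comparator will be usual care, as routinely provided in the NHs where the study takes place". Section 8.6 allows control treatments to be modified or stopped and says that interventions outside the deprescribing plan are not collected.

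**The concern.** Two separate routes to bias run through one task.

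- **Information about controls.** The study itself has the pharmacist produce a report naming the flagged drugs of each control, at the start of the 16 weeks over which change is measured. That pharmacist is then discussing deprescribing for other residents with the same NH's nurses and physicians. Nothing in the text tells the pharmacist to hold a control's report back. If reports prompt changes in controls, the difference between arms shrinks, and because such interventions are not collected, the cause could not be identified afterwards.
- **Open entries.** A STOPP/START flag depends on the pathologies entered as well as on the drugs. The person entering them knows the allocation and, in the intervention arm, is scoring the result of their own review. If the entries change between the two runs, the PIM count can change with no drug changed.

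The same PIM status also feeds the secondary outcome on potentially inappropriate DDDs (9.2.2.1).

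**Working it through.** **Tracing the steps**

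| Step | Who | Blinded? | Arms |
|---|---|---|---|
| Medication review (8.1.1) | NH pharmacist | No | Intervention |
| Tool run, Visit 1 (9.2.1, 9.3.1) | NH pharmacist | No | Both |
| Tool run, Visit 2 (9.2.1, 9.3.2) | NH pharmacist | No | Both |
| Transcription and totals (9.2.1) | Investigators | No | Both |
| Analysis (6.2.2) | Statistician | Yes | Receives finished data |

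The drugs can be cross-checked, because the medication plan is taken from the NH record (12.1.2) and uploaded. For the pathologies, the text describes neither an upload nor a fixed list. The website stores nothing after a run (9.2.1), and the tool's output form is the source document (12.1.2). Central checking covers coherence and plausibility only (12.2.4). No masked repeat is described.

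**The plan's own figure.** Section 11.2 expects half of 18 NHs, a mean of 59 beds and 20% recruitment: 9 × 59 × 0.20 = 106.2, which reproduces its 106. That is 53 per arm, about 106 / 9 / 2 = 5.9 controls per NH, and 106 × 2 = 212 tool runs at most. (Separately, the synopsis pairs 106 with 10 NHs of 50 beds, which gives 10 × 50 × 0.20 = 100, the figure in 6.1. These should be reconciled.)

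**Illustration of size.** The documents state no SD, effect, alpha or power. I assume a two-sided 0.05 test, 53 per arm, a normal approximation, and no clustering or dropout.

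*Contamination.* The standardised effect detectable with 80% power is (1.960 + 0.842) × √(2/53) = 0.544. If controls obtain a fraction c of it, power is Φ(0.544(1 − c)/√(2/53) − 1.960), and the sample size that restores 80% is multiplied by 1/(1 − c)².

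| c | Power | Multiplier for N |
|---|---|---|
| 0 | 80% | 1.00 |
| 0.1 | 71% | 1.23 |
| 0.2 | 61% | 1.56 |
| 0.3 | 50% | 2.04 |
| 0.5 | 29% | 4.00 |

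*Differential entry.* Suppose there is no true effect and the mean change in one arm is shifted by u PIMs through entries alone. With SE = SD × √(2/53), the false-positive rate is Φ(u/SE − 1.960) + Φ(−u/SE − 1.960). For example, with SD 1, SE = 0.194; u = 0.25 (one flag in every four participants) gives u/SE = 1.287 and a rate of 25.1%.

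| u | SD 1 | SD 1.5 | SD 2 |
|---|---|---|---|
| 0.10 | 8.1% | 6.4% | 5.8% |
| 0.25 | 25.1% | 13.8% | 9.9% |
| 0.50 | 73.0% | 40.4% | 25.1% |

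The first route pulls the estimate toward zero. The second can push it either way. The tables show sensitivity to each; they do not estimate what will happen.

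**The case against.** The case for leaving the plan alone has several parts.

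- *Contamination would occur anyway.* Randomisation is within NH, one team treats both arms, and usual care deliberately includes the earlier deprescribing consensus (3.6). A tool printout is also far short of the intervention, which comprises a review, propositions, team discussion, a plan and the participant's validation. This largely stands. A reader might infer that controls receive part of the intervention, but the documents do not say that the pharmacist shares or acts on a control's report. What remains is that the study generates that report itself and could avoid doing so.
- *PIM knowledge may come earlier.* Section 7.2 ranks residents by number of regular drugs, then describes the eligible list as ordered by PIM use. If the second wording is literal, flags on future controls exist before Visit 1. That stands, and it calls for reconciling 7.2 alongside the fix.
- *Review knowledge cancels.* In the intervention arm Visit 1 follows the review, so what the pharmacist learned is available at both runs and tends to drop out of a change score. This stands. Bias needs entries that change between runs, which the text permits but does not show.
- *Self-medication.* A reader might infer that self-medication, listed only in the intervention arm (6.1), inflates that arm's count. The documents do not support this: the endpoint is drugs prescribed (5.1), counted from the medication plan in the NH record, and the self-medication list feeds the review.
- *Masking the investigators is not realistic.* They generate the randomisation lists (6.2.1), follow progress weekly (8.4) and extract data from deprescribing plans (9.2.3.1). This stands; coded labels give partial masking only. The reason in 6.2.2 is true of the dataset as a whole, although the medication plan and PIM report are collected in both arms.

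The annexes were not available to me. The report example or the CRFs (Annexes 9 to 11) may already record the pathologies entered.

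**Conclusion.** The concern holds as a matter of who does what. One unblinded person delivers the intervention, produces a PIM report on every participant in both arms at both visits, and makes the pathology entries on which the primary outcome depends, with no rule in the text fixing them between runs. The consequences are possible, not shown.

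It is tempting to conclude that the bias favours the intervention. The documents do not support that: contamination works against the intervention, no direction of entry error is documented, and the net effect cannot be determined. The figures above rest wholly on assumed inputs. Under them, a modest degree of either problem matters in a trial of 106: power of 61% to 50% if controls obtain 20% to 30% of the effect, or a false-positive rate of about 10% to 25% for a 0.25-PIM shift. The plan should be changed because the change is cheap, not because a bias has been demonstrated.

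**What to change.** **Change**

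1. In 9.2.1, 9.3.1 and 9.3.2, remove the PIM assessment from the NH pharmacist's visit tasks; the pharmacist uploads the dated medication plan at each visit. Adjust 9.2.5 (death or hospitalisation) and the source-document entry in 12.1.2 to match.
2. On the inclusion CRF, before allocation, record one pathology list per participant from the NH record.
3. After Visit 2, the investigators, who already transcribe every plan, run the tool for both time points, on one tool version and with the same pathology list, adding only dated new diagnoses. They work from coded plans without arm labels where feasible.
4. State in 6.2.2 that this masking is partial, because the investigators hold data that reveal allocation.
5. Reconcile the two ranking criteria in 7.2, so that PIM information on future controls is not generated at screening.

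The medication review in the intervention arm is untouched.

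**Cost.** This is protocol and CRF wording, with no added visits or staff. Up to 212 tool runs move to the investigators. One short pathology list per participant is collected, which should be checked against the category A justification in 2.2, since that relies on not collecting broad health data. Queries about why a drug was prescribed become harder to resolve. Full masking would need a separate assessor; this change does not claim it.
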